	
treatment, investigator's decision to withdraw the patient, patient withdraws consent, pregnancy of the patient, noncompliance with trial treatment or procedure requirements, or administrative reasons.
 
After the end of treatment, each patient will be followed for 30 days for adverse event monitoring (serious adverse events will be collected for 90 days after the end of treatment with investigator attribution as to whether the SAE is associated with MK-3475 or subsequent therapies). After the Post-Treatment Safety Follow-Up Visit, patients will be followed for survival via phone contact every 12 weeks.
 
Patients who discontinue study therapy without documented disease progression should continue to be monitored for disease status by radiologic imaging according to the guidelines described in the Study Schema for post-treatment follow-up.

--	--

Overall Trial Schema (PD1 Trial Timeline_v10Jun16)

Patient Visit Timeline (dosing, scans and biomarkers)

[figure not shown]
[figure not shown]

TABLE OF CONTENTS

1.	OBJECTIVES	10
1.1	Primary Objectives.....	10
1.2	Secondary Objectives.....	10
1.3	Exploratory Objectives	10
2.	BACKGROUND	11
2.1	Study Disease.....	11
2.2	CTEP IND Agent: MK-3475	19
2.3	Other Agent(s): N/A	23
2.4	Rationale for Trial of MK-3475 in Merkel Cell Carcinoma Patients	23
2.5	Correlative Studies Background	26
3.	PATIENT SELECTION	31
3.1	Eligibility Criteria	31
3.2	Exclusion Criteria	33
3.3	Inclusion of Women and Minorities	36
4.	REGISTRATION PROCEDURES	36
4.1	Investigator (IVR), Non-Physician Investigator (NPIVR), and Associate Plus (AP) Registration with CTEP	36
4.2	Site Registration.....	38
4.3	Patient Registration.....	39
4.4	General Guidelines.....	40
5.	TREATMENT PLAN.....	41
5.1	Agent Administration.....	42
5.2	Definition of Dose-Limiting Toxicity: N/A.....	50
5.3	General Concomitant Medication and Supportive Care Guidelines	50
5.4	Duration of Therapy.....	51
5.5	Duration of Follow Up.....	52
5.6	Criteria for Removal from Study	53
5.7	Criteria to Resume Treatment.....	53
5.8	Treatment Beyond Progression.....	54
5.9	Discontinuation of Treatment Following Complete Response.....	55
5.10	Retreatment with MK-3475 of patients with recurrence	55
5.11	Beginning and End of the Trial.....	56
6.	DOSING DELAYS/DOSE MODIFICATIONS	56
6.1	MK-3475 Dose Modifications	56
6.2	Delayed Visits for Reasons Other Than Toxicity.....	70
7.	ADVERSE EVENTS: LIST AND REPORTING REQUIREMENTS	70

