- Serum, plasma, and PBMC storage
- Optional tumor biopsy/tissue collection (core biopsy, punch biopsy or excisional biopsy) if PD is confirmed.

End of Therapy

- (The End of Therapy Visit is performed as soon as possible following the decision to stop study drug treatment or in conjunction with last treatment visit if discontinuation of therapy is anticipated).
- Concomitant medications
- Review of AEs
- Physical exam
- Vital signs and weight
- 12-lead EKG
- Performance status
- Laboratory tests:
 - Urine or serum HCG in women
 - CBC with differential
 - Comprehensive serum chemistry panel
- Laboratory tests (if not collected at time of determination of CR, PR, or disease progression):
 - Kyn/Trp ratio
 - INF- γ ELISpot
 - Immunophenotyping
 - T cell gene expression and phenotyping
 - MCPyV antibody levels
 - Serum, plasma, and PBMC storage
- Tumor imaging (not required if scan was performed within prior 4 weeks).
- Optional tumor biopsy/tissue collection if safe and feasible (core biopsy, punch biopsy or excisional biopsy), in patients who have not achieved CR (either responding, stable or progressing lesions) ([Section 2.5.1](#)).

Post-Treatment Follow-Up

Post-Treatment Safety Follow-Up (30 Days Post Treatment \pm 3 days). (This visit may be combined with End of Treatment Visit if decision to discontinue treatment is delayed).

- Concomitant medications
- Review of AEs
 - All AEs occurring within 30 days after the last dose of study treatment will be reported. Serious adverse events (SAE) related and unrelated to trial treatment will be collected for 90 days after the last dose of trial treatment or the start of new anticancer treatment, whichever comes first. Afterwards, only SAEs that are related to trial treatment will be reported.
- Physical exam
- Vital signs and weight
- Performance status
- Laboratory tests:
 - Complete blood count (CBC) with differential
 - Comprehensive serum chemistry panel
 - Urinalysis
 - T3, FT4, and TSH

Post-Treatment Disease Assessments

- Upon discontinuation of treatment in patients without documented progression, radiologic imaging for disease assessment will continue either at the investigative site or locally. Imaging will be collected and evaluated per RECIST 1.1.
- Year 1 Post-Treatment: Imaging will be performed Q 3 months (+/-14 days) or as clinically indicated for the first year post-completion of treatment.

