- Years 2 and 3 Post-Treatment: Imaging will be performed Q 6 months (\pm 1 month) or as clinically indicated during years 2 and 3 post-treatment.
- If the study remains open, imaging will be performed annually or as clinically indicated once patient has completed 3 years of follow up for disease assessment.
- Collection of standard of care disease assessments will continue until progression, start of a new anticancer therapy, death or end of study, whichever occurs first.

Survival Follow-Up Phone Contacts (every 12 weeks \pm 1 week)

Begin survival follow-up phone contacts after discontinuing MK-3475 due to disease progression or start of a new anticancer therapy (initiate 12 weeks \pm 1 week following the Post-Treatment Safety Follow-Up Visit). Survival follow-up will continue until death or the end of the study, whichever occurs first.

5.1.2 ***Other Agent(s): N/A***

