Additionally, immune-related adverse events (irAEs), defined as adverse events of unknown etiology, associated with drug exposure and consistent with an immune phenomenon, may be predicted based on the nature of the MK-3475 compound, its mechanism of action, and reported experience with immunotherapies that have a similar mechanism of action. Special attention should be paid to AEs that may be suggestive of potential irAEs. An irAE can occur shortly after the first dose or several months after the last dose of treatment. All AEs of unknown etiology associated with drug exposure should be evaluated to determine if they are possibly immune-related. If an irAE is suspected, efforts should be made to rule out neoplastic, infectious, metabolic, toxin or other etiologic causes prior to labeling an adverse event as an irAE.

The table below includes guidelines for managing irAEs that are not listed in the AE-specific table (see [section 6.1.2](#)).

General Dose Modification Guidelines for Drug-Related Immune-Related Adverse Events

irAE	Withhold/Discontinue MK-3475?	Supportive Care
Grade 1	No action	Provide symptomatic treatment
Grade 2	May withhold MK-3475	Consider systemic corticosteroids in addition to appropriate symptomatic treatment
Grade 3 and Grade 4	Withhold MK-3475 Discontinue if unable to reduce corticosteroid dose to < 10 mg per day prednisone equivalent within 12 weeks of toxicity	Systemic corticosteroids are indicated in addition to appropriate symptomatic treatment. May utilize 1 to 2 mg/kg prednisone or equivalent per day. Steroid taper should be considered once symptoms improve to Grade 1 or less and tapered over at least 4 weeks.

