- a. In general, safety labs and assessments/procedures are to be performed on Day 1 and before the first dose of treatment for each cycle unless otherwise specified. In general, the window for each visit is ± 3 days unless otherwise noted. Treatment cycles are 3 weeks (21 days); however the treatment cycle interval may be increased due to toxicity according to the dose-modification guidelines provided in Section 6. If the interval is increased, all procedures except imaging should be performed based on the new dosing schedule.
- b. MK-3475 will be administered as an IV infusion over 30 minutes. The dose is 2mg/kg every 3 weeks (21 days ± 3 days). The infusion is given in an out-patient setting. Patients who restart treatment after relapse from CR should resume at the same dose and cycle interval which they were receiving before discontinuation.
- c. Blood for correlative studies will be drawn on Day 1 of Cycle 1, prior to drug administration, then prior to study drug infusion on day 1 of Cycle 2 and Cycle 5, then prior to drug administration every 3rd cycle (i.e., day 1, Cycle 8, 11, 14, etc.) during first year of treatment. After 1 year of therapy, blood for correlative studies is also drawn upon confirmed CR or PR and at the time of disease progression. If the correlative blood draw is not obtained at time of determination of CR, PR or disease progression, then this collection will be done at the end-of-therapy visit.
- d. AEs and laboratory safety measurements will be graded per NCI CTCAE version 5.0. All AEs, whether gradable by CTCAE or not, will also be evaluated for seriousness.
- e. Record all AEs occurring within 30 days after the last dose of trial treatment. Report all SAEs (related and unrelated to trial treatment) occurring up until 90 days after the last dose of trial treatment or the start of new anticancer treatment, whichever comes first. Afterwards, report only SAEs that are related to trial treatment.
- f. Vital signs to include temperature, pulse, respiratory rate, weight, and blood pressure. Height will be measured at baseline only.
- g. EKG should be performed at baseline, and then within 30 minutes of the end of infusion after dosing for Cycle 1 and Cycle 8 and at discontinuation.
- h. Laboratory tests for screening are to be performed within 14 days before the first dose of trial treatment. See [Section 5.1.1](#) for details regarding laboratory tests.

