- q. Tumor biopsy tissue (archival or fresh) is required per screening requirements. In patients who have not achieved CR (either responding, stable or progressing lesions), a biopsy sample of a tumor may be obtained if feasible and safe (core, punch or excisional biopsy). This post-treatment biopsy is highly preferred, but optional.
- r. After the start of new anticancer treatment or documented disease progression, the patient should be contacted by telephone every 12 weeks \pm 1 week to assess for survival status. Survival follow-up will continue until death or end of the study, whichever occurs first.
- s. Laboratory tests for determining eligibility for retreatment in patients who relapse from CR are to be performed within 7 days before the first retreatment dose of MK-3475. See Section [3.1.6](#) for details regarding laboratory tests.
- t. Patients who attain a CR and discontinue treatment or those who attain a PR or SD after completion of 2 years of treatment may restart trial treatment if they meet the criteria specified in [Section 5.4.3](#).
- u. After cycle 1, limited physical exam performed on visits not correlated with scans.
- v. For patients with a history of pulmonary disease, prolonged smoking history, or symptoms of respiratory dysfunction.

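### In patients who stop for progression or start new therapy, no scheduled contact asks about serious adverse events after the day-30 visit, although SAEs are to be collected to day 90

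*Combined protocol and SAP*

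**What the plan says.** **Collection rule.** Section 5.1.1 says that SAEs, whatever their attribution, "will be collected for 90 days after the last dose of trial treatment or the start of new anticancer treatment, whichever comes first". Footnote e of the Section 10 calendar repeats it: "Report all SAEs (related and unrelated to trial treatment) occurring up until 90 days after the last dose of trial treatment", with the same cut-off at new treatment. After that, only treatment-related SAEs are reported. The Study Summary (Duration of Participation) is worded differently: "serious adverse events will be collected for 90 days after the end of treatment with investigator attribution as to whether the SAE is associated". That sentence goes on to name the study drug and later therapies as possible causes, and it gives no cut-off at new treatment.

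**Schedule after stopping.** Section 5.1.1 places the safety visit about 30 days after the last infusion and lists it with a window of ± 3 days. For patients who stop because of progression or start new therapy, survival phone contacts then begin: "initiate 12 weeks \pm 1 week following the Post-Treatment Safety Follow-Up Visit". Footnote r describes their purpose. After progression or new treatment, "the patient should be contacted by telephone every 12 weeks", to establish survival status.

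**Calendar marks after end of treatment (the same in the Year 1 and Year 2 tables).**

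| Column | Who attends | *Review of AEs* | *Concomitant Medications* |
|---|---|---|---|
| Safety follow-up | all who stop | marked | marked |
| Disease assessments | stopped without progression | marked, footnote e | blank |
| Survival follow-up | after progression or new therapy | blank | marked |

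**The concern.** A collection rule works only if someone asks. For patients who stop for progression, the last scheduled adverse-event review is at about day 30, and the next contact comes after the 90-day window has ended and is not marked for adverse events. Whether late SAEs are actively sought therefore depends on why treatment stopped.

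This matters because Section 6.1.1 itself warns that "An irAE can occur shortly after the first dose or several months after the last dose of treatment". Adverse events and SAEs are the primary safety endpoints (Section 13.3.2), and better safety information is part of the stated reason for enlarging the trial to 50 patients (Sections 2.4.1 and 13.5). If events after day 30 are missed, the overall late-SAE count is too low.

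**Working it through.** The plan states no figure for this gap, so there is none to reproduce. The check is calendar arithmetic with the last dose as day 0.

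**Inputs**
- Safety visit: day 30 ± 3, so day 27 to 33 (Section 5.1.1).
- First survival call: 12 weeks ± 1 week after that visit, so 84 days, range 77 to 91 (Section 5.1.1).
- SAE window: 90 days after the last dose, or new anticancer treatment if earlier (Section 5.1.1; footnote e).
- Post-treatment imaging without progression: every 3 months ± 14 days in the first year (Sections 5.1.1 and 5.5; footnote o).

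**Day of the first call** = safety visit + interval
- Nominal: 30 + 84 = 114
- Earliest: 27 + 77 = 104
- Latest: 33 + 91 = 124

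All three fall after day 90.

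**Part of the window after the last adverse-event review** = 90 − day of safety visit
- Nominal: 90 − 30 = 60 days (60/90 = 67%)
- Range: 90 − 33 = 57 days (63%) to 90 − 27 = 63 days (70%)

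This is the figure for a patient who has not started new treatment by day 90. For one who starts on day *t*, between the safety visit and day 90, the all-SAE gap is *t* − 30. With *t* = 45, for example, it is 15 days.

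**Does the choice of anchor change the answer?**
- The calendar counts the safety visit from discontinuation instead of the last infusion. Assume discontinuation falls 0 to 28 days after the last dose. The nominal visit is then on day 30 to 58 and the nominal call on day 114 to 142, which leaves 90 − 58 = 32 to 90 − 30 = 60 days without a scheduled question.
- Footnote r can be read as counting the 12 weeks from documented progression. Assume progression falls between 28 days before and 21 days after the last dose. The nominal call is then on day −28 + 84 = 56 to 21 + 84 = 105, possibly inside the window. Section 5.1.1 is explicit that the count starts at the safety visit, and on either reading the call is for survival status.

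**Comparison group.** Three months is about 91 days, so the first post-treatment assessment without progression falls on about day 77 to 105. That column carries adverse-event review under footnote e.

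**The case against.** The strongest reply is that the gap is narrower, and its effect less certain, than the dates suggest. Several stronger inferences that a reader might draw are not supported.

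- **That 60 of 90 days applies to every patient who stops for progression.** It does not. Under Section 5.1.1 and footnote e the all-SAE window closes at new anticancer treatment, and treatment stops for progression that warrants alternative therapy. About 60 days is the upper end (63 at the edge of the visit window). Related SAEs remain reportable after new treatment starts, still without a scheduled question.
- **That late SAEs surface only if patients volunteer them.** This is too strong. Section 7.3.3 obliges investigators to report SAEs immediately, requires expedited reporting of deaths on study, and its note 1 sets timelines for attributed SAEs beyond 30 days. Sites can learn of hospital admissions and deaths without a study call. The cover is partial, though. The table is headed for events within 30 days of the last administration, and note 1 covers only SAEs with possible, probable or definite attribution. Unrelated SAEs on days 31 to 90 are within the collection rule but outside that expedited route.
- **That the survival call excludes SAEs.** The calendar is better described as incompletely marked. Concomitant medications are marked for the call, and Section 5.3.1 and footnote m tie medications taken after day 30 to SAE recording. This suggests that SAE capture was in mind, but no adverse-event question is scheduled.
- **That a planned comparison is biased.** None is planned by reason for stopping. Section 13.5.2 summarises events as counts and frequencies by grade. What is at risk is completeness of the overall count.
- **That the call's lateness is the main defect.** A call just after day 90 also comes after the window has ended. Either call could ask back over the whole period, so the missing question is the main defect. Earlier timing only shortens recall.
- **That the roughly 4-week half-life (Section 2.2.1.1) sizes the loss.** It makes late events plausible but says nothing about how many are missed.

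**Conclusion.** The point holds as a gap in active ascertainment. Followed as written, the schedule does not ask patients who stop for progression about SAEs after about day 30, although the protocol requires collection to day 90. The uncovered stretch is up to about 60 of the 90 days (57 to 63 across the visit window), less where new treatment closes the all-SAE window early. It is 32 to 60 days if the safety visit is counted from discontinuation, under the assumed delay of 0 to 28 days.

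Under-ascertainment of late SAEs in this group is probable, on the assumption that passive reporting misses some events that a direct question would find. Its size cannot be computed, because the documents give no SAE rate for days 31 to 90. The documents do not show that late SAEs go unreported, and neither the primary response analysis nor any planned comparison is affected. This is a worthwhile, low-cost improvement to safety data collection.

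**What to change.** 1. In both Section 10 tables, mark *Review of AEs* (footnote e) in the Survival Follow-up column.
2. In Section 5.1.1 (Survival Follow-Up Phone Contacts) and footnote r, state that the first call asks for all SAEs since the safety visit, up to the end of the collection window (in the present Section 5.1.1 text, day 90 or the start of new anticancer treatment). State that later calls ask for treatment-related SAEs.
3. Optionally, move the first call to shortly after day 90 to shorten recall. No extra contact is needed.
4. Reconcile the Study Summary, whose 90-day window has no cut-off at new treatment, with Section 5.1.1 and footnote e. In the same amendment, align the anchors for the safety visit (last infusion or discontinuation) and for the first call (safety visit or progression).

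The cost is amendment wording, one CRF question and a slightly longer call. The Study Summary reports enrolment in the past tense, so the benefit is limited to patients still on treatment, retreated or in follow-up. For those already past the window, a look-back question at the next call can recover some events, with longer recall.

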5.2 Definition of Dose-Limiting Toxicity: N/A

5.3 General Concomitant Medication and Supportive Care Guidelines

5.3.1 MK-3475 Concomitant Medication

Medications or vaccinations specifically prohibited in the exclusion criteria are not allowed during the ongoing trial. If there is a clinical indication for one of these or other medications or vaccinations specifically prohibited during the trial, discontinuation from trial therapy or vaccination may be required. The investigator should discuss any questions regarding this with CTEP. The final decision on any supportive therapy or vaccination rests with the investigator and/or the subject's primary physician; however, the decision to continue the subject on trial therapy or vaccination schedule requires the mutual agreement of the Investigator, CTEP, and the patient.

Acceptable Concomitant Medications

All treatments that the investigator considers necessary for a patient's welfare may be administered at the discretion of the investigator in keeping with the community standards of medical care. All concomitant medication will be recorded on the case report form (CRF) including all prescription, over-the-counter (OTC), herbal supplements, and IV medications and fluids. If changes occur during the trial period, documentation of drug dosage, frequency, route, and date may also be included on the CRF.

All concomitant medications received within 28 days before the first dose of trial treatment and 30 days after the last dose of trial treatment should be recorded. Concomitant medications administered after 30 days after the last dose of trial treatment should be recorded for SAEs.

Prohibited Concomitant Medications

Patients are prohibited from receiving the following therapies during the Screening and Treatment Phase (including retreatment for post-complete response relapse) of this trial:

- Anti-cancer systemic chemotherapy or biological therapy.
- Immunotherapy not specified in this protocol.
- Chemotherapy not specified in this protocol.
- Investigational agents other than MK-3475.
- Radiation therapy
 - o Note: Radiation therapy to a symptomatic solitary lesion or to the brain may be allowed after consultation with Protocol P.I and CITN. Any lesion treated with radiation can no longer be considered as a target lesion for evaluating MK-3475 efficacy.
- Live vaccines within 30 days prior to the first dose of trial treatment and while participating in the trial. Examples of live vaccines include, but are not limited to, the following: measles, mumps, rubella, chicken pox, yellow fever, rabies, BCG, and typhoid (oral) vaccine. Seasonal influenza vaccines for injection are generally killed virus vaccines and are allowed; however, intranasal influenza vaccines (e.g. Flu-Mist[®]) are live attenuated vaccines, and are not allowed.
- Glucocorticoids for any purpose other than to modulate symptoms from an event of suspected immunologic etiology. The use of physiologic doses of corticosteroids may be

approved after consultation with the Protocol P.I.

Patients who, in the assessment by the investigator, require the use of any of the aforementioned treatments for clinical management should be removed from the trial. Patients may receive other medications that the investigator deems to be medically necessary.

The Exclusion Criteria describes other medications which are prohibited in this trial. There are no prohibited therapies during the Post-Treatment Follow-up Phase.

